#### 10.2.3 Phone calls (Visit 4, 6, 8, 10, 12 and 14)

The patient will be contacted every 3rd months by a study nurse. A visit window of  $\pm 21$  days is allowed. The following will be reviewed every 3rd months;

- Assess AEs
- Compliance check
- Record concomitant medication

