#### 10.2.4 Treatment visits (Visit 5, 7, 9, 11, 13, 15)

The patient will visit the site every 6 months. A visit window of  $\pm 21$  days is allowed. Follow-up is otherwise according to standard national guidelines.

---

The following assessments will be performed during the treatment visits;

- Assess AEs
- Record concomitant medication
- Compliance and drug accountability check
- Provide the patient with IMP for 6 months + 1 week (not applicable for visit 15)

In addition to the items that will be performed during the treatments visits, the following will be performed at the time of visit 7 and 15 (after 1 and 3 years);

- CT/MRI (Magnetic Resonance Imaging) thorax and abdomen
- CEA (Optional)

In case of any recurrence the patient will be taken care of according to standard treatment at the site and will be withdrawn from further study treatment.

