4.8 Trial assessments

Written informed consent is given by the patient in the first screening visit, which takes place before or shortly after surgery (allowing for randomization to be performed within 12 weeks from surgery).

In the second screening visit, which takes place after surgery, inclusion and exclusion criteria are assessed in patients with tumors harboring somatic alterations in the PIK3CA, PIK3R1 or PTEN genes. Patients without such somatic alterations, and patients not fulfilling all inclusion criteria, or fulfilling at least one exclusion criteria are excluded from the trial. However, patients with regular use of ASA (>3 doses/week) fulfilling all other eligibility criteria, are included in an observational arm.

Randomization takes place in the third visit, in which the subject is also provided with IMP for 200 days. The treatment period begins at the randomization visit and ends after 3 years.

A phone contact is made with the subject three months from randomization, and thereafter every sixth month. Also, subjects visit their respective site every sixth month from randomization, i.e,. the subjects are in contact with the site every third months for three years. At the end of the follow-up period, five years from randomization, there is an additional visit or phone contact for subjects who have completed three years in the trial (up to and including Visit 15). The trial assessments, starting from randomization, are visualized in Figure 2, and described in detail in Table 4.

[figure not shown]

Figure 2. Time-line of trial assessments. The dice icon refers to Randomization, the phone icon to Phone contact, the human icon to Clinic visit, and the skeleton icon to clinic visit including examination with CT/MRI.

Table 4. Overview of trial assessments

Assessment/Visit	Random- ization (R)	First phone call	First site visit	Subsequent phone calls	Subsequent site visits	Final visit/phone call
Visit no.*	3	4	5	6, 8, 10, 12, 14	5, 7, 9, 11, 13, 15	16
Timepoint	0	3mo after R	6mo after R	Every 6mo after first phone call	Every 6mo after first site visit	5y from R
Visit/call window	-	±21 days	±21 days	±21 days	±21 days	±30 days
Provide with IMP	Yes		Yes		Yes	
Assess AEs		Yes	Yes	Yes	Yes	
Subject asked about compliance		Yes	Yes	Yes	Yes	
Remaining pill count			Yes		Yes	
Record concomitant medication		Yes	Yes	Yes	Yes	
CT/MRI of thorax and abdomen					Yes (visit 7 and 15 – 1y and 3y after R)**	

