4.8.1 Trial assessments during the COVID-19 pandemic

From April 4th, 2020, most clinic visits are switched to phone contacts, and subjects are provided with IMP by mail. Subjects are asked about their compliance at each phone contact, and remaining pills are counted whenever the subject has a possibility to visit the clinic. Remaining pill count is then retrospectively entered into the eCRF for each clinic visit that has been replaced with a phone contact. Study personnel have been encouraged to go back to clinic visits as the COVID-19 spread has decreased.

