4.8.2 Treatment compliance

Every sixth month, subjects are provided with two boxes of IMP, each containing 100 pills. Subjects are to take one pill per day. Subjects treated with adjuvant chemotherapy, who, for medical reasons, should not receive ASA during said treatment are allowed to start taking the IMP after termination of chemotherapy. Subjects are also allowed to pause taking the IMP for up to 30 days in a row during the trial. All treatment pauses, for any reason, are entered with a start and end date in the eCRF.

At each phone contact and clinic visit, the subject is asked how often they forget to take the IMP, with response options

- Never/Rarely
- Once in a while
- Sometimes
- Often
- Always.

At each clinic visit, the subject brings the IMP packages provided to them at the preceding clinic visit, the remaining pills are counted mechanically and the sum is entered into the eCRF.

Compliance until the last clinic visit (C_{LCV}) will be calculated as

$$C_{LCV}$$
 % = $\frac{DP \text{ before the final clinic visit - RP up to and including the final clinic visit}}{TD until the final clinic visit - number of days on allowed break before the final clinic visit} •100,$

where DP refers to the total number of dispensed pills, RP to the total number of remaining pills, and TD to the total number of potential treatment days. The number of days on break before the final clinic visit only includes breaks that are maximum 30 days or related to adjuvant chemotherapy, i.e. breaks that are allowed by the study protocol.

Subjects with an EoS event before the first clinic visit, in which the first pill count takes place, but after the first phone contact, will not have any pill counts in the eCRF. However, they will have been asked at the first phone contact (Visit 4) how often they forget to take the IMP. Compliance until Visit 4 (C_{V4}) for these subjects will be defined as 80 % if the response is "Never/Rarely" or "Once in a while", and 0 % if the response is "Sometimes", "Often", or "Always". C_{LCV} (or C_{V4}) for subjects with visits outside of the allowed time-window of ± 21 days will be calculated similarly as if their visits had been within the allowed time-window.

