Subjects leaving the trial for any reason between two clinic visits, or between the first phone contact and the succeeding clinic visit, will not have a compliance measurement for the time between the last clinic visit (or Visit 4) and trial exit. For these subjects, an assumption on how long C_{LCV} (or C_{V4}) is assumed valid must be made. Denote the last date for which C_{LCV} (or C_{V4}) is assumed valid $D_{LCV/V4}$. For subjects experiencing recurrence, death, or other cancer, $D_{LCV/V4}$ will be defined as the date of last IMP intake, if such a date is registered in the eCRF, or the event date (see Section 6.2.1 for definition), whichever comes first. For subjects leaving the trial before an endpoint or before trial completion, $D_{LCV/V4}$ will be defined as the date of last IMP intake, if such a date is registered in the eCRF, or the Visit 15 date/EoS date, whichever comes first. For subjects completing 3 years in the trial, $D_{LCV/V4}$ will be defined as the date of Visit 15 (the 3-year follow-up clinic visit). The number of days for which C_{LCV} (or C_{V4}) will be assumed valid will be calculated as days from randomization until $D_{LCV/V4}$, subtracting the number of days on treatment breaks (before $D_{LCV/V4}$) not allowed by the protocol (see above), for each randomized subject having received the IMP at least once.

For subjects reaching a trial endpoint, days from $D_{LCV/V4}$ until the event date will be defined as having 0 % compliance. Similarly, for subjects leaving the trial before completion, days from $D_{LCV/V4}$ until 3 years from randomization will be defined as having 0 % compliance. For all subjects, regardless of trial completion or exit, days on treatment breaks (before $D_{LCV/V4}$) not allowed by the study protocol will be defined as having 0 % compliance. Overall compliance (OC) will be calculated as a weighted average between C_{LCV} (or C_{V4}) and 0, as follows

OC % =
$$\frac{\text{Valid days*C}_{\text{LCV or V4}} + \text{Zero-compliance days*0}}{\text{Valid days+Zero-compliance days}}.$$

Subjects with an EoS event before the first phone contact will not have answered the question on frequency in taking the IMP, or have any pill counts in the eCRF, hence, it is not possible to calculate compliance for such subjects.

See 6.2.2 for derivation of the variables needed for compliance calculation.

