6.2.2 Variables for compliance calculation

See Section 4.8.2 for the definition of overall compliance.

The number of treatment days until the last clinic visit will be calculated as days from the date of randomization (*A_randomiseringsdatum*) until the date of the last clinic visit (*V_Visitdatum* for the latest clinic visit, where clinic visits are *V_Visit* V5, V6, V7, V8, V9, V10, V11, V13, V15).

The number of dispensed pills at a certain clinic visit will be calculated as 100 times the number of unique package numbers (*S_Package_Number*) for packages that are not shredded (*R2465T32612_MAKULERAD*) or not found at the clinic (*S_Not_Found*).

The total number of dispensed pills will be calculated as the sum of the dispensed pills at each visit.

The total number of remaining pills will be calculated as the sum of the number of remaining pills for each clinic visit (S_returned_number). If the package was lost by the subject (S_Lost_Drug="True"), and S_returned_number equals 0 or "NA", the number of remaining pills for that package will be defined as 100, to not overestimate compliance.

The number of days on break will be calculated as the sum of days from $V_UppehallFromDatum$ until $V_UppehallTomDatum$, for all visits where $V_Uppehall=1$. Treatment breaks that are longer than 30 days and unrelated to adjuvant chemotherapy will be defined as non-compliant with the study protocol. Similarly, breaks that are at most 30 days of related to chemotherapy will be defined as compliant with the study protocol. Days on treatment break that are overlapping with a later registered treatment break will be subtracted.

Compliance for subjects with an EoS event after the first phone contact but before the first clinic visit will be based on the variable *V_LMIntag* for *V_Visit*=V4.

The date for which C_{LCV} (or C_{V4}) is considered valid until ($D_{LCV/V4}$) is $E_sistaintag$, dfs_event_date , $E_endofstudydtm$, or $v15_visitdatum$. The number of valid days will be calculated as the number of days from randomization ($A_randomiseringsdatum$) until $D_{LCV/V4}$, subtracting the number of days on non-allowed treatment break (see above). The number of zero-compliance days will be calculated as days from $D_{LCV/V4}$ until $E_endofstudydtm$ or 3 years from randomization, adding the number of days on non-allowed treatment break.

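### SAP 6.2.2 lists phone contacts V6, V8 and V10 as clinic visits, so compliance can be mis-scored for a few subjects with events in the exploratory per-protocol sets

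*SAP*

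**What the plan says.** **Visit types.** Protocol 10.2.3 is headed "Phone calls (Visit 4, 6, 8, 10, 12 and 14", and what is reviewed there includes a compliance check but no drug accountability. Protocol 10.2.4 places the "Compliance and drug accountability check" at the six-monthly treatment visits V5, V7, V9, V11, V13 and V15. SAP Table 4 uses the same split and shows "Remaining pill count" for site visits only. SAP 4.8.2 agrees: "At each clinic visit, the subject brings the IMP packages provided to them at the preceding clinic visit, the remaining pills are counted mechanically".

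**The list.** SAP 6.2.2 computes treatment days up to the last clinic visit and names the clinic visits as "V5, V6, V7, V8, V9, V10, V11, V13, V15".

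**Compliance up to the last clinic visit (C_LCV, SAP 4.8.2).** This is pills dispensed before that visit (DP), minus pills remaining up to and including it (RP), divided by treatment days to that visit (TD) less allowed breaks. In 6.2.2, "The total number of remaining pills will be calculated as the sum of the number of remaining pills for each clinic visit". A package flagged lost, with a returned number of zero or missing, counts as 100 remaining. No rule covers a package that is neither counted nor flagged lost.

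**After the last visit.** SAP 4.8.2 recognises that subjects who leave between clinic visits "will not have a compliance measurement for the time between the last clinic visit (or Visit 4) and trial exit". It carries C_LCV forward to a defined date and averages in zero-compliance days to give overall compliance, which sets the 80% flag for PP3 and PP5.

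**Text pointing the other way.** Protocol Figure 2 marks the compliance and accountability check at every contact from V4 to V15.

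**The concern.** The date of the last clinic visit fixes TD and the cut-offs for DP and RP. If a phone contact is taken as that visit, the supply handed out at the preceding site visit enters DP and the days run on to the call, but Table 4 provides no count to set against it. C_LCV then depends on how a missing count is coded, which the SAP does not say.

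SAP 5.2.2 keeps an early leaver in PP3 only if the subject reached an endpoint. Subjects who complete three years have V15 as their last visit, so the list does not affect them. The list error therefore falls on subjects with events, and adherence could be judged by a different yardstick according to outcome.

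**Working it through.** **Inputs.** 200 pills per six-month supply and the C_LCV formula (SAP 4.8.2); visit months from Protocol Figure 2; 80% threshold (SAP 5.2.2); 18% three-year risk on placebo, risk ratio 0.38 and 135 per arm after drop-out (SAP 4.5.2). The documents give no compliance example to reproduce.

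**Assumptions.** Visits on schedule, no breaks, constant adherence a, half-year of 182.5 days, no count at the phone contact. Let k be the number of counted site visits before the call (V6: 1, V8: 2, V10: 3). Then TD = 182.5k + 91.25 and DP = 200(k+1). The counted remainder is k(200 - 182.5a).

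**Uncounted pills scored as taken:** C_LCV = [200(k+1) - k(200 - 182.5a)] / TD.
- V6, a = 0.6: (400 - 90.5)/273.75 = 113%
- V8, a = 0.6: (600 - 181)/456.25 = 92%
- V10, a = 0.6: (800 - 271.5)/638.75 = 83%

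**Uncounted pills scored as untaken:** C_LCV = 182.5ka/TD = a·k/(k + 0.5).

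| Last listed visit | Taken, a = 0.6 | Taken, a = 1 | Lowest a reaching 80%, taken | Untaken, a = 1 | Lowest a reaching 80%, untaken |
|---|---|---|---|---|---|
| V6 | 113% | 140% | 10% | 67% | none (120%) |
| V8 | 92% | 124% | 45% | 80% | 100% |
| V10 | 83% | 117% | 57% | 86% | 93% |

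If the missing count is left missing, C_LCV cannot be computed. Stopping at the last counted visit gives 60% at a = 0.6 and 100% at a = 1 in all three cases.

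**From C_LCV to the 80% flag.** Overall compliance equals C_LCV times the share of days that are not zero-compliance days. A score of 82.7% at V10 drops below 80% once that zero share exceeds 1 - 80/82.7 = 3.3%, or about 21 to 24 days of 639 to 730. At V8 the share is 1 - 80/91.8 = 12.9%, and at V6 it is 1 - 80/113.1 = 29%. The pass thresholds in the table hold only with no zero-compliance days.

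**How many subjects.** With exponential timing (assumption), 25% of three-year recurrences fall in months 9-12, 15-18 and 21-24. For Mutation A that is 0.252 × 24.3 = 6.1 on placebo and 0.251 × 9.2 = 2.3 on ASA. Clustering of detections at the scans would change this share; deaths and other cancers would add to the number. Suppose pills are scored as taken, a fraction q = 10-30% of subjects have 60% adherence, and a share s = 5-25% of events fall in the windows (assumptions). Then 24.3·q·s = 0.1 to 1.8 placebo subjects with events are wrongly admitted.

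**Direction.** Take the same coding, and suppose non-adherent subjects have 18% risk in both arms. The PP risk is then 0.18[(1-q)+qs]/[(1-q)+0.18qs] on placebo. On ASA the first (1-q) in the numerator is multiplied by 0.38. A true ratio of 0.38 among adherent subjects reads:
- q equal in both arms: 0.383 (q = 0.1, s = 0.05) to 0.440 (q = 0.3, s = 0.25)
- q = 0.1 on ASA, 0.3 on placebo, s = 0.25: (0.367/0.9045)/(0.775/0.7135) = 0.374
- q = 0.3 on ASA, 0.1 on placebo, s = 0.25: (0.341/0.7135)/(0.925/0.9045) = 0.467

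The ratio can move either way.

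**The case against.** **SAP 4.8.2 already governs.** Section 6.2.2 refers to 4.8.2 for the definition of compliance, and there a clinic visit carries a mechanical count. A programmer who follows 4.8.2 avoids the error. This stands as a reason for low severity. But 6.2.2 is the variable-level specification and says otherwise in so many words.

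**Counts may exist at these contacts.** Figure 2 allows it, and a real count there would give the right score. SAP 4.8.1 also lets pandemic-period pills be counted whenever the subject can attend. This stands: the contradiction is certain, the mis-scoring conditional. The retrospective-entry rule does not account for the list, because it concerns clinic visits turned into calls: "Remaining pill count is then retrospectively entered into the eCRF for each clinic visit that has been replaced with a phone contact". Neither source explains why V12 and V14 are left out.

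**Safeguards.** Population membership is assigned before the blind is broken (SAP 5.2), and a second statistician reviews the data-processing code (SAP section 9). A score of 113-140% would probably be noticed; one of 83% or 92%, or a falsely low one, would not stand out.

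**Stronger readings that the documents do not support.** A reader might infer that any shift is toward the null and so harmless. That needs similar non-adherence in both arms, and the working shows the ratio falling below 0.38 without it. A reader might infer that three-year completers are always scored correctly. That is true of the list error only; a package neither counted nor flagged lost could also affect a completer. A reader might infer that the main results are at risk. They are not: the primary endpoint and secondary endpoints 1-5 use the full analysis population.

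**Conclusion.** Minor. The list in SAP 6.2.2 contradicts SAP Table 4, SAP 4.8.2 and protocol 10.2.3/10.2.4, and this is certain. Whether it changes any score depends on three things: the list being followed literally, no count at the contact, and how the missing count is coded. Given those, C_LCV can cross 80% in either direction, although zero-compliance days pull overall compliance down from the figures shown.

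In PP3 the list error is confined essentially to subjects with an endpoint in three quarter-year windows. On planning figures that is about six exposed recurrences on placebo and two on ASA in Mutation A, and only some of these would be misclassified. The documents do not give the actual number, and the direction of any shift in the PP estimate is not determined. The analyses touched are optional, exploratory and reported without p-values (SAP 8.3).

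**What to change.** 1. In SAP 6.2.2, replace the list with V5, V7, V9, V11, V13 and V15, or define the last clinic visit as the last visit with a recorded pill count. DP, RP and TD then all stop at that visit, and C_LCV is carried forward as 4.8.2 already states.
2. Before unblinding, add one rule for a package dispensed before that visit that is neither counted nor flagged lost. It should treat pills and days alike, for example by removing its pills from DP and its days from TD. Removing the pills alone would create a new error: a fully adherent completer with one of six supplies uncounted would score 5 × 182.5/1095 = 83%, and with two uncounted 4 × 182.5/1095 = 67%.
3. Reconcile Protocol Figure 2 with protocol 10.2.3/10.2.4 and SAP Table 4 on where accountability is checked.

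The cost is a corrected list, one added sentence and a consistency note. No new data are needed.

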5.2.2 Per protocol populations

The per protocol population at 3 years (PP3) consists of all subjects in the FAP who had at least 80 % compliance, fulfill all eligibility criteria, no significant protocol violations, and have either reached a study endpoint (recurrence, other cancer, or death) within 3 years, or completed at least 3 years in the trial.

The per protocol population at 5 years (PP5) consists of all subjects in the FAP who had at least 80 % compliance, no significant protocol violations, fulfill all eligibility criteria, and have either reached a study endpoint (recurrence, other cancer, or death) within 5 years, or completed at least 5 years in the trial.

Subjects who are thought to fulfil all eligibility criteria at randomization, but later are found not to fulfil all eligibility criteria will be excluded from the PP3 and PP5, for example subjects where Lynch syndrome is discovered after randomization.

Significant protocol violations include more than 12 weeks from surgery until randomization, leaving the study because of pregnancy, lack of compliance with the study protocol, wanting to leave the study, refusal to cooperate, other medical reasons, e.g. initiating another treatment not compatible with ASA, or leaving the trial because of an SAE/AE.

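### Pill-count compliance has no 100% ceiling, so a subject on IMP for under 80% of days can enter PP3; the lost-box rule, whose effect depends on event time, needs a sensitivity version

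*SAP*

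**What the plan says.** **Supply and intake.** SAP 4.8.2 states that every sixth month "subjects are provided with two boxes of IMP, each containing 100 pills", and "Subjects are to take one pill per day". SAP 4.8 agrees for the randomization visit: "the subject is also provided with IMP for 200 days".

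**Formula.** In 4.8.2, C_LCV is dispensed pills (DP) minus remaining pills (RP), divided by treatment days (TD) less allowed breaks, up to the last clinic visit: "RP to the total number of remaining pills, and TD to the total number of potential treatment days". Neither 4.8.2 nor 6.2.2 limits the result to 100%. "Overall compliance (OC) will be calculated as a weighted average between" C_LCV, applied to the days on which it is assumed valid, and zero for the remaining days. For a subject with an event, the valid days end at the last recorded intake or at the event, whichever is earlier.

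**Lost boxes.** Under 6.2.2, if a box is flagged as lost and its returned number is 0 or missing, "the number of remaining pills for that package will be defined as 100, to not overestimate compliance".

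**Use.** SAP 5.2.2 requires at least 80% compliance for PP3 and PP5. The threshold is the same for completers and for subjects who "have either reached a study endpoint (recurrence, other cancer, or death) within 3 years".

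**Self-report.** "At each phone contact and clinic visit, the subject is asked how often they forget to take the IMP". The compliance score uses this answer only for subjects who leave between Visit 4 and the first clinic visit. They score 80% or 0%.

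**The concern.** The two parts of the rule err in opposite directions, and both can decide who is in the per-protocol set.

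- **No ceiling.** A tablet dispensed and not returned counts as taken. A fully adherent subject has about 18 left over per period. If these are not brought back, C_LCV exceeds 100%, and the excess cancels days that the SAP itself scores as zero. The plan's stated aim with lost boxes is to avoid overestimating compliance, but here it leaves an overestimate open.
- **Fixed penalty.** A lost box costs 100 tablets however long the subject was followed. The same loss weighs more when follow-up was cut short by an event, so PP3 membership depends partly on event time. The first scheduled trial CT/MRI, at Visit 7 (month 12), lies inside the affected window.

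The planned weights do not repair this. SAP 8.3 models treatment received from baseline covariates, not inclusion in PP3, and it rejects censoring weights.

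**Working it through.** The documents give no compliance figure to reproduce, so this is direct arithmetic on the formulas in 4.8.2 and 6.2.2.

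**1. No ceiling**

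Inputs: 200 tablets per period and one per day (4.8.2); Visit 5 at about day 182, window ±21 days (Table 4); threshold 80% (5.2.2).

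Suppose Visit 5 is the last counted visit, intake was full to that point and no surplus was returned:

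- C_LCV = 200/182 = 109.9%.
- IMP stops on day 243. Recurrence is on day 330, before Visit 7, with end of study recorded that day.
- Valid days = 243; zero-compliance days = 330 − 243 = 87.
- Share of days on IMP = 243/330 = 73.6%.
- Overall compliance = 243/330 × 200/182 = **80.9%**, so the subject is in PP3.
- With the 18 surplus tablets returned, or with a cap, C_LCV = 182/182 = 100% and overall compliance = **73.6%**, so the subject is out.

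In this situation the effective threshold is 0.80 × 182/200 = 72.8% of days on IMP. If Visit 5 falls on day 161 (182 − 21), it is 0.80 × 161/200 = 64.4%.

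**2. Lost box**

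For a fully adherent subject, C_LCV = (T − x)/T. T is treatment days to the last clinic visit, and x is the tablets taken from the lost box but scored as untaken. A six-month interval is 182.6 days. With two boxes and no replacement, x therefore lies between 182.6 − 100 = 82.6 and 100.

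| Last clinic visit | T (days) | x = 100 | x = 82.6 | At 80% |
|---|---|---|---|---|
| Month 6 | 183 | 45.2% | 54.8% | out |
| Month 12 | 365 | 72.6% | 77.4% | out |
| Month 18 | 548 | 81.7% | 84.9% | in |
| Month 24 | 730 | 86.3% | 88.7% | in |
| Month 36 | 1096 | 90.9% | 92.5% | in |

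- Break-even is T = x/0.20: 500 days (16.4 months) for x = 100, or 413 days (13.6 months) for x = 82.6. With six-monthly counts, month 18 is the first visit that passes in either case.
- For x = 100 the visit window does not change this: month 12 is at most 74.1% and month 18 at least 81.0%.
- With an assumed 183-day allowed chemotherapy break, month 18 gives 72.6% and month 24 gives 81.7%, so the cut-off moves to month 24.
- A completer loses 100/1096 = 9.1 points and needs true compliance of 80 + 9.1 = 89.1% to stay in. True 90% scores 80.9% (in); true 85% scores 75.9% (out).

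**3. Events in the affected window**

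Inputs: three-year recurrence of 18% on placebo and 0.38 × 18% = 6.84% on ASA (SAP 4.5.2). I assume exponential times, which ignores any bunching at the month-12 scan.

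- Placebo, months 6-18: 0.82^(6/36) − 0.82^(18/36) = 0.9675 − 0.9055 = 0.0619.
- ASA: 0.9316^(6/36) − 0.9316^(18/36) = 0.9883 − 0.9652 = 0.0231.
- The sum is 0.0850, giving 11.5 events at 135 per arm or 12.7 at 150.
- At an assumed 5-10% of these subjects losing a box, 0.6 to 1.3 events are affected.

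**4. Visit list**

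Section 6.2.2 counts V6, V8 and V10 as clinic visits; Table 4 makes them phone contacts. Take the list literally, with no pill count at V6 (day 273.9). A fully adherent subject with one lost box then scores (400 − 117.4)/273.9 = 103.2%. The discrepancy therefore changes which months are affected, and it also produces values above 100%.

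**The case against.** **The lost-box rule has a sound purpose.** Every package number adds 100 to dispensed tablets. If a full box is lost and replaced in the first period, the rule gives (300 − 118)/182 = 100%; without it the score would be (300 − 18)/182 = 155%. Treating lost boxes as uncounted is also imperfect, because a box that really was unused would be scored too high. This stands, and it is why the rule should be kept.

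**Unreturned surplus is an assumption.** Subjects bring packages back for counting (SAP 4.8.2), and Protocol 10.7.4 requires discrepancies to be explained. This also stands: no frequency is given.

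**The no-ceiling case depends on timing.** A reader might infer that it works for any subject who stops early. It does not. With IMP stopped on day 270, recurrence on day 365 and Visit 7 counted, C_LCV = (400 − 112)/365 = 78.9% and overall compliance = 270/365 × 78.9% = 58%, so the subject is out. The case needs an event before the next count. The subject must also not have left by choice, for an adverse event or for non-compliance, since 5.2.2 makes those exits protocol violations.

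**Other stronger readings that the documents do not support:**

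- *That a lost box removes every adherent subject with an event before month 18.* Between Visit 4 and the first clinic visit the score is self-report, and before Visit 4 none can be calculated.
- *That no compliant completer is removed.* Those with true compliance from 80% to just under 89.1% are.
- *That the per-protocol event rate is lowered.* Completers receive 12 boxes, against 2-4 for a subject last seen at Visit 5 or 7. At an illustrative 2% loss per box, the chance of any loss is 1 − 0.98^12 = 22% against 4-8%. The net direction is open.

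**Conclusion.** The concern holds as a small point with two parts.

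**Missing ceiling.** The formula as written lets C_LCV reach about 110% at Visit 5 and so admits a subject on IMP for 73.6% of days against the SAP's own 80% threshold. This rests on surplus tablets going unreturned and on the event falling before the next pill count. The number of such subjects cannot be computed from the documents.

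**Lost-box rule.** It makes PP3 membership depend on event time for fully adherent subjects with events between about the month-6 and month-18 clinic visits, provided the box was used and not replaced. At design rates and an assumed 5-10% loss rate, about one event is at stake. No direction of bias is shown.

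Only PP3 and PP5 are affected. Under SAP 8.3 these analyses are optional, exploratory and reported without p-values, although Protocol 10.13.6 plans analyses on both FAP and PP. The FAP primary and secondary analyses do not use compliance. The rule is the same in both arms, and SAP 5.2 assigns membership before the blind is broken.

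**What to change.** 1. **Cap C_LCV at 100%** before it enters overall compliance. This is one line in 4.8.2 and one line of code, and I see no downside. It removes only the excess above 100%: missed tablets that were thrown away still count as taken, as in any pill count.
2. **Keep the lost-box rule and add a sensitivity version of PP3 and PP5** that treats lost boxes as uncounted. State exactly how many treatment days leave the denominator with each box, because a box may cover about 82 or 100 of the 182 days. If no box was counted in a period, use that visit's adherence answer, as the SAP already does at Visit 4. The cost is a little more analysis work, and a lost box that really was unused is scored too high in that version.
3. **Reconcile the clinic-visit list in 6.2.2 with Table 4** in the same edit.

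All three belong before population membership is fixed. If that has already happened, report the per-protocol results both ways.
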